10 EFFICACY ANALYSIS

[figure not shown]
Unless otherwise indicated, efficacy endpoints will be summarized and analyzed using the FAS by visit and treatment group, as applicable.

10.1 Primary Efficacy Endpoint

The primary efficacy endpoint is percent change from Baseline in SALT I at Week 24.

SALT I is a well-validated metric and widely utilized tool for determining the degree of hair loss based on the percentage of scalp surface area involved on the top, back, and each side of the scalp for AA. Using the diagram in [Figure 2](#), the Investigator will determine the percent scalp hair loss in a given quadrant, multiply this by the total scalp area delineated by that quadrant, and sum the resultant numbers for each quadrant to give the total percent scalp hair loss with a maximum score of 100. Change and percent change from Baseline in total percent of scalp hair loss will then be calculated as described in [Section 4.1](#).

Figure 2: Visual Aid for Estimating Percentage Scalp Hair Loss Using the Severity of Alopecia Tool

Analysis of Primary Efficacy Endpoint

Primary Analysis

Missing data will be handled as described in Section 5.3.

Percent change from baseline in SALT I score will be summarized using descriptive statistics by visit and treatment group. Observed and change from Baseline in SALT I score will be summarized similarly.

The primary endpoint will be analyzed using a MMRM model. The MMRM model will include the treatment group (2 mg, 3 mg, and placebo), analysis visit (Weeks 1, 2, 4, 8, 12, 16, 20, and 24), and treatment-by-analysis visit interaction as fixed effects, and disease duration (years; refer to Section 5.2) and Baseline SALT I score as covariates.

An unstructured (UN) variance-covariance matrix will be specified for the MMRM model. If convergence issues arise, the autoregressive (order 1) [AR(1)] structure will be used. If the AR(1) structure also does not converge, other covariance structures deemed appropriate to fit the data will be used and the structure with the smallest finite-sample corrected Akaike

Information Criteria (AAIC) value will be retained. Least squares (LS) mean estimates, LS mean differences between treatment groups (each of the active arms versus placebo only), corresponding 95% CIs, and p-values will be reported for each visit. The primary comparisons of interest will be between each active arm and placebo at Week 24.

Sensitivity Analysis

In addition to the primary analysis, the following sensitivity analyses will be performed using imputed data or alternative analysis set:

1) ANCOVA at Week 24 with Multiple imputation (MI) using the FAS

All missing SALT I scores at scheduled visits up to Week 24 will be imputed using a multiple imputation (MI) technique with a fully conditional specification (FCS; Brand, 1999; van Buuren et al., 2007) predictive mean matching (PMM; Heitjan and Little, 1991; Schenker and Taylor, 1996) sequential regression multiple imputation model, where missing values for all variables (visits) are imputed sequentially one at the time, with preceding variables (visits) serving as covariates. For each variable (visit), the FCS PMM regression model will include the outcome at that visit as the dependent variable and as independent variables, the treatment group, disease duration, baseline SALT I score, and SALT I scores at the previous scheduled visits using a seed of 20210106. The number of observed values whose predicted values are closest to the predicted value of the missing value and among which an observed value will be randomly selected to impute the missing value will be the SAS default value (i.e., k = 5). This process will be repeated 100 times, resulting in a total of 100 complete analysis datasets.

The example SAS code for the multiple imputation process is as below:

```
PROC MI DATA=SALTI1 OUT=SALTI2 SEED=20210106 NIMPUTE=100;
CLASS TRTPN;
FCS REGPMM (SALT2=TRTPN DISDUR BASESALT);
FCS REGPMM (SALT3=TRTPN DISDUR BASESALT SALT2);
FCS REGPMM (SALT4=TRTPN DISDUR BASESALT SALT2 SALT3);
FCS REGPMM (SALT5=TRTPN DISDUR BASESALT SALT2 - SALT4);
FCS REGPMM (SALT6=TRTPN DISDUR BASESALT SALT2 - SALT5);
FCS REGPMM (SALT7=TRTPN DISDUR BASESALT SALT2 - SALT6);
FCS REGPMM (SALT8=TRTPN DISDUR BASESALT SALT2 - SALT7);
VAR TRTPN DISDUR BASESALT SALT2 - SALT8;
RUN;
```

For each multiply imputed dataset, percent change from Baseline in SALT I score will be derived using observed and imputed values and the percent change from Baseline at Week 24 will be analyzed using an ANCOVA model including the treatment group as fixed effect, and disease duration (years) and Baseline SALT I score as covariates. Results from each ANCOVA model (LS means [and associated standard errors], LS mean difference between each etrasimod treatment group and placebo [and associated standard errors], and parameter estimates) will be

combined and reported along with two-sided 95% CI and p-value using PROC MIANALYZE based on Rubin's rule.

- 2) Observed Cases (OC) in mFAS: The primary analysis of the primary endpoint will be repeated in mFAS based on observed data without imputation.
- 3) OC in PPS: The primary analysis of the primary endpoint will be repeated using the PPS to evaluate the influence of major protocol deviations on the primary results.
- 4) OC in Randomized Set: The primary analysis of the primary endpoint will be repeated in Randomized Set based on observed data without imputation.
- 5) OC in FAS Adjusting for the SALT I Stratification Variable and Cohort: The primary analysis of the primary endpoint will be repeated using the FAS based on observed data without imputation and will also include the stratification variable of SALT I (< 50 and \geq 50) and cohort (1 and 2) as fixed effects to evaluate the influence of the change of randomization ratio between Cohort 1 and Cohort 2.
- 6) OC in FAS Including Cohort 2 Only: The primary analysis of the primary endpoint will be repeated using the FAS based on observed data without imputation but including only subjects randomized in Cohort 2. The stratification variable of SALT I (< 50 and \geq 50) will also be included in the MMRM model as a fixed effect.
- 7) OC in FAS Excluding the Etrasimod 3 mg Treatment Group: The primary analysis of the primary endpoint will be repeated using the FAS based on observed data without imputation but excluding the Etrasimod 3 mg treatment group. The stratification variable of SALT I (< 50 and \geq 50) and Cohort (1 and 2) will also be included in the MMRM model as a fixed effect.

Subgroup Analyses

Subgroup analyses will be performed descriptively for the subgroups defined in Section 5.7.

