10.3.1. Severity of Alopecia Tool

To participate in this study, a subject must have moderate-to-severe AA as assessed by a SALT I score of ≥ 50 (Cohort 1) and ≥ 25 and < 95 (Cohort 2) at Screening and Day 1/Baseline as described in Section 4.1.

SALT I is a well-validated metric and widely utilized tool for determining the degree of hair loss based on the percentage of scalp surface area involved on the top, back, and each side of the scalp for AA. Using the diagram in [Figure 2](#), the Investigator will determine the percent scalp hair loss in a given quadrant, multiply this by the total scalp area delineated by that quadrant, and sum the resultant numbers for each quadrant to give the total percent scalp hair loss with a maximum score of 100 ([Olsen 2004](#)). SALT I scores at Screening, Baseline, and Week 24 will also be assessed by central review.

Figure 2: Visual Aid for Estimating Percentage Scalp Hair Loss Using the Severity of Alopecia Tool

Source: (Olsen 2004).

The SALT I will be assessed at timepoints according to the Schedules of Assessments (Appendix 1 and Appendix 2).

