4.4 Descriptive Statistics

All continuous variables will be summarized by presenting the number of subjects, mean, SD, median, minimum, and maximum. Categorical variables will be summarized using frequencies and percentages. Summary tables will be presented by treatment and visit, when applicable.

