4.6 Software Version

All analyses will be performed using SAS[®] software Version 9.4.

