5 STATISTICAL CONSIDERATIONS

5.1 Analysis Sets

The following analysis sets will be defined for the DB Treatment Period and OLE Period separately:

Table 2. Summary of Analysis Sets

Analysis Set	Description
DB Treatment Period	
Randomized Set	
The Randomized Set includes all randomized subjects, irrespective of whether they received any study drug.
 
All subjects will be analyzed according to the treatment group to which they were randomized.

Full Analysis Set (FAS)	
The FAS includes all randomized subjects with a SALT I < 95 at Baseline who received at least one dose of study drug. The FAS will be used for the primary analysis of the primary efficacy endpoint and main analysis of the secondary, exploratory, and other efficacy endpoints.
 
All subjects will be analyzed according to the treatment group to which they were randomized.

Modified Full Analysis Set (mFAS)	
The mFAS consists of all randomized subjects with a SALT I < 95 at Baseline who received at least 1 dose of study drug, have a Baseline measurement, and have at least 1 post-randomization measurement.
 
The mFAS is endpoint specific, therefore subjects included in the analysis set for 1 endpoint may differ from another endpoint, based on the Baseline and post-Baseline data. The mFAS will be used for sensitivity analyses for the primary and secondary endpoints in SALT I.
 
All subjects will be analyzed according to the treatment group to which they were randomized.

Analysis Set	Description
Per Protocol Set (PPS)	
The PPS consists of all subjects in the FAS with no major protocol deviations (PD) potentially having an impact on the SALT I-related primary and secondary efficacy endpoints (refer to Sections 7.2 and 10.1).
 
The PPS will be used for sensitivity analyses for the primary and secondary efficacy endpoints in SALT I to evaluate the influence of major PD potentially having an impact on the efficacy endpoints.
 
All subjects will be analyzed according to the treatment group to which they were randomized.

Safety Set (SAF)	
The SAF consists of all randomized subjects who received at least 1 dose of study drug.
 
All safety analysis in the DB Treatment Period will be performed using SAF. All subjects will be analyzed according to the actual treatment they received. In case a subject received more than one actual treatment, the first treatment received will be used for the safety analysis.

OLE Period	

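### The first fallback for a non-converging MMRM is plain AR(1), which forces one variance on all visits; if the SD of percent change rises over time, the Week 24 interval would be too narrow

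*SAP*

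**What the plan says.** SAP 10.1 analyses percent change in SALT I with an MMRM over "analysis visit (Weeks 1, 2, 4, 8, 12, 16, 20, and 24"), starting from an unstructured matrix. The next step is fixed: "If convergence issues arise, the autoregressive (order 1) [AR(1)] structure will be used". Only after that does the choice widen: "If the AR(1) structure also does not converge, other covariance structures deemed appropriate to fit the data will be used", with the smallest corrected AIC deciding among them. AR(1) is not qualified as heterogeneous, and no step checks whether it fits. SAP 4.6 names the software: "All analyses will be performed using SAS" (version 9.4). Protocol 11.6 specifies the unstructured matrix and gives no fallback.

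The primary comparisons are each active arm against placebo at Week 24, the last visit, but LS means, differences, "corresponding 95% CIs, and p-values will be reported for each visit". Sensitivity analyses 2 to 7 repeat this MMRM in other analysis sets or with added terms. Sensitivity analysis 1 is a Week 24 ANCOVA after multiple imputation and does not use this covariance.

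The Week 1 visit exists in Cohort 2 only (SAP 3.4). SAP 5.1 defines the main analysis set: "The FAS includes all randomized subjects with a SALT I < 95 at Baseline who received at least one dose of study drug". Protocol 10.3.1 required a "SALT I score of ≥ 50 (Cohort 1) and ≥ 25 and < 95 (Cohort 2"), so an unstated number of Cohort 1 subjects fall outside the FAS.

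**The concern.** The unstructured matrix for eight visits has 8 × 9 / 2 = 36 parameters; plain AR(1) has 2. The rule therefore jumps past every structure that lets the variance differ by visit. A two-parameter model will rarely fail to converge, so the step after AR(1) is unlikely to be reached.

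Percent change is zero at Baseline by construction, so its spread may well grow with time on study. A common variance would then average the Week 24 variance down with the smaller early ones. The 95% CI at the visit of primary interest would be too narrow, and the intervals at the earliest visits too wide. With no formal testing strategy, estimates and intervals are the main product of this trial, so interval width matters. Because sensitivity analyses 2 to 7 inherit the rule, agreement among analyses that had all fallen back would not reveal the problem.

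**Working it through.** **Inputs from the documents (SAP 3.2).** SD 17.8 at Week 24, the only SD given; difference 20; 20, 5 and 10 Cohort 2 completers on 3 mg, 2 mg and placebo; two-sided 0.05; 15% dropout.

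**The plan's own figure.** Two-sample t-test power from the noncentral t:
- 3 mg: SE = 17.8 × √(1/20 + 1/10) = 6.89; noncentrality 20/6.89 = 2.90; 28 df; power 79.97%.
- 2 mg: SE = 17.8 × √(1/5 + 1/10) = 9.75; noncentrality 2.05; 13 df; power 47.6%.

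These agree with the stated 80% and 47%, so 17.8 is the right anchor for Week 24.

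**Effect of AR(1), if used.** Assumptions: SD linear in weeks from a chosen Week 1 value to 17.8; correlation exp(−gap/20) or exp(−gap/60), gap in weeks; Week 1 observed in 100%, 70% or 42/78 of subjects. The large-sample AR(1) fit minimises log|V| + trace(V⁻¹Σ), where Σ is the assumed true covariance. The Week 24 SE ratio is the fitted SD divided by 17.8. The error rate of a nominal 5% test is 2[1 − Φ(1.96 × ratio)].

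| Assumed Week 1 SD | Fitted common SD | Week 24 SE ratio | Nominal 5% becomes |
|---|---|---|---|
| 5 | 12.05-12.65 | 0.677-0.711 | 0.16-0.18 |
| 9 | 13.51-13.90 | 0.759-0.781 | 0.13-0.14 |
| 14 | 15.81-15.96 | 0.888-0.897 | about 0.08 |
| 17.8 (constant) | 17.80 | 1.000 | 0.05 |
| 22 (falling) | 20.02-20.15 | 1.125-1.132 | about 0.027 |

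Hand check: the root mean square of the eight SDs is 15.69 on the path from 14 (15.69/17.8 = 0.88) and 11.41 on the path from 5 (11.41/17.8 = 0.64). Both are near the fitted values and in the same direction.

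**How likely the fallback is.** The share of the FAS without a Week 1 visit depends on how many Cohort 1 subjects have SALT I below 95, which the documents do not give: 36/78 = 46% if all, 18/60 = 30% if half, 9/51 = 18% if a quarter. Unstructured REML fits to simulated data (15% dropout, Week 1 SD 5 or 14, 100-iteration limit, not SAS) failed as follows:
- FAS, N = 51, 60 or 78: 0 of 720.
- Cohort 2 only, N = 42: 0 of 240.
- Sensitivity analysis 7 (3 mg group removed), N = 27, 36 and 54: 10, 12 and 27 of 240, or 4-11%.

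In analysis 7 only the planned Cohort 2 subjects on 2 mg and placebo, 6 + 12 = 18, can have a Week 1 value. A second fit of that design with a different optimiser, also not SAS, gave near-singular results in 2, 2 and 1 of 60 runs. The failure rate there is therefore uncertain.

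**Alternatives.** Over 20 assumed covariance patterns, the large-sample Week 24 SE ratio was:

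| Structure | Parameters | Ratio |
|---|---|---|
| First-order antedependence, ANTE(1) | 8 + 7 = 15 | 1.00 |
| Heterogeneous compound symmetry | 8 + 1 = 9 | 0.93-1.08 |
| Heterogeneous AR(1) | 8 + 1 = 9 | 0.86-1.11 |
| Heterogeneous Toeplitz | 8 + 7 = 15 | 0.83-1.11 |

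ANTE(1) frees every visit's variance and every adjacent correlation, so a ratio of 1.00 with complete data is nearly automatic. In 1,000 simulated trials per setting (N = 60, 15% dropout, Cohort 1 without Week 1) it gave 3.8-4.6% false rejections throughout. That simulation was of the FAS, not of analysis 7.

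**The case against.** The strongest reply is that the trigger was not seen where it would matter most: no unstructured failure appeared in the simulated primary FAS model or in Cohort 2 alone. This stands. A reader might infer that the primary 3 mg result is likely to carry an interval about 30% too narrow, or an error rate near 18%. The documents do not support that. It needs both an unstructured failure in the FAS and an assumed 3.6-fold rise in SD (5 to 17.8). Failures appeared only in sensitivity analysis 7, which has no 3 mg arm and for which no error rate under AR(1) has been worked out.

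The rise itself is also undocumented. Week 1 values come only from Cohort 2, which admits SALT I from 25. Percent change divides by Baseline, so the same rating noise is larger in percentage terms at low scores, and this could lift the Week 1 SD. A rise remains plausible, but its size is unknown.

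Finally, the plan has safeguards. Sensitivity analysis 1 uses the Week 24 variance. SAP 5.6 makes all comparisons exploratory. SAP 4.4 would expose a rise in the by-visit tables: "All continuous variables will be summarized by presenting the number of subjects, mean, SD, median, minimum, and maximum". These limit the consequence, but the tables by treatment would show the problem only after unblinding, with no remedy specified.

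**Conclusion.** The point holds conditionally. Two things must both happen: the unstructured model fails, and the SD of percent change rises over visits. The Week 24 SE is then too small, by about 10-11% from an assumed Week 1 SD of 14 and about 29-32% from 5. With a constant SD there is no distortion; with a fall from 22 the SE is about 13% too large. All SDs before Week 24, and the correlations, are assumptions.

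The fallback looks unlikely for the primary analysis and more plausible in sensitivity analysis 7. The defect is the single variance. Having a fixed fallback order is good practice and is not criticised here. This is an optional, cheap improvement.

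**What to change.** Before unblinding, replace the AR(1) fallback in SAP 10.1 with:

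> If the unstructured model does not converge, a structure with a separate variance at each visit will be used: first-order antedependence [ANTE(1)], then, if that does not converge, heterogeneous compound symmetry. Homogeneous AR(1) will be used only if neither converges, with an observed-case Week 24 ANCOVA in the same analysis set reported alongside.

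Apply the same rule to sensitivity analyses 2 to 7. ANTE(1) comes first because it also suits visits that are 1, 2 and 4 weeks apart. Heterogeneous compound symmetry comes next because, of the remaining heterogeneous structures tried, its ratio stayed closest to 1.

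The cost is a few lines of SAP text and code. If the fallback is used and variance rises, Week 24 intervals will be wider than under AR(1). If heterogeneous compound symmetry is reached, the Week 24 SE may still be off by about 7-8% in either direction.

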3.2 Sample Size

Subjects will be randomized as follows:

- Cohort 1: ~36 subjects in 2:1 randomization ratio (~24 subjects to etrasimod 2 mg and ~12 subjects to placebo)
- Cohort 2: ~42 subjects with SALT I < 95 at Baseline in 4:1:2 randomization ratio (~24 subjects to etrasimod 3 mg, ~6 subjects to etrasimod 2 mg, and ~12 subjects to placebo)

Assuming a 15% drop-out rate from the study over 24 weeks, at least 35 treatment completers (20 subjects to etrasimod 3 mg, 5 subjects to etrasimod 2 mg, and 10 subjects to placebo from Cohort 2; plus subjects from Cohort 1 with SALT I < 95 at Baseline) at Week 24 will provide at least 80% and 47% power to detect a treatment difference of 20% for etrasimod 3 mg and etrasimod 2 mg from placebo, respectively, in the percent change from Baseline in SALT I at Week 24 by a 2-sample t-test using a 2-sided significance test level of 0.05 and common standard deviation (SD) of 17.8%.

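### Sensitivity analysis 2 must reproduce the primary treatment differences, and no planned analysis of the continuous SALT I endpoints varies the missing-at-random assumption

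*SAP*

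**What the plan says.** SAP 5.1 defines the primary analysis set: "The FAS includes all randomized subjects with a SALT I < 95 at Baseline who received at least one dose of study drug". The mFAS repeats those conditions and adds that subjects "have a Baseline measurement, and have at least 1 post-randomization measurement". SAP 5.3 leaves missing continuous data unimputed for the primary MMRM and refers to 10.1 and 10.2 for sensitivity analyses with imputation.

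SAP 10.1 then lists seven sensitivity analyses:

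- Analysis 1 imputes: "All missing SALT I scores at scheduled visits up to Week 24 will be imputed using a multiple imputation (MI) technique". The imputation model uses treatment group, disease duration, baseline SALT I and earlier SALT I scores. An ANCOVA follows, and results are combined by Rubin's rule.
- Analysis 2 is the MMRM in the mFAS: "The primary analysis of the primary endpoint will be repeated in mFAS based on observed data without imputation".
- Analyses 3 to 7 refit the observed-data MMRM in the PPS, in the Randomized Set, with stratum and cohort added, in Cohort 2 only, and without the 3 mg arm.

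SAP 10.2 reuses the list for change from Baseline in SALT I. For the responder endpoints, the main analysis counts missing subjects as non-responders (NRI), and it is repeated with multiple imputation (MI) and with observed cases. LOCF and WOCF appear in the SAP abbreviation list, but no analysis uses them.

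**The concern.** Two things are at issue. First, a table that cannot differ from the primary result is presented as a check on it (Table 14.2.1.2.2 in SAP Appendix 3), and a reader may take the agreement as support.

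Second, the MMRM estimate depends on MAR: given the model covariates and a subject's own earlier scores, unobserved Week 24 values behave like observed ones in the same arm. Departures are conceivable. Protocol 8.1 lists stopping criteria tied to lymphocyte count and cardiac monitoring, and Protocol 1.2 describes effects of this drug class on both, so the reasons for leaving could differ by arm. If etrasimod subjects who leave do worse than their earlier scores predict, the primary analysis and analysis 1 would both miss it, and nothing planned for the continuous endpoints would show by how much.

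**Working it through.** **Step 1: does analysis 2 use different data?** Set the two definitions side by side.

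| Condition | FAS (SAP 5.1) | mFAS (SAP 5.1) |
|---|---|---|
| Randomized, Baseline SALT I < 95 | yes | yes |
| At least one dose | yes | yes |
| Baseline value | implied by SALT I < 95 | yes |
| At least one post-randomization value | not required | required |

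Only the last row separates the sets. A subject with no post-randomization SALT I has no outcome row in an observed-data MMRM, so the model, rows and estimates are the same. As a check, an unstructured-covariance repeated-measures model (three arms, eight visits, baseline and duration as covariates) was fitted to one simulated trial. The FAS (n = 78) and the mFAS (n = 73) both gave Week 24 differences from placebo of -12.678 (SE 5.699) for 2 mg and -18.358 (SE 6.008) for 3 mg. The largest discrepancy was 0.0.

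**Step 2: does any other analysis relax MAR?** Analysis 1 imputes within the subject's own arm from covariates and earlier visits, with no shift: MAR. Analyses 3 to 7 are observed-data MMRMs: MAR.

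A two-visit simulation shows the consequence. It had 24 active and 12 placebo subjects, with 4 and 2 missing the final visit, and 3,000 replicates per row. Active-arm missing values were made worse than MAR predicts by delta.

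| Delta | Difference with full data | MAR likelihood | MI + ANCOVA |
|---|---|---|---|
| 0 | -20.1 | -20.1 | -19.5 |
| 10 | -18.4 | -20.1 | -19.5 |
| 20 | -16.8 | -20.2 | -19.5 |
| 30 | -15.2 | -20.2 | -19.6 |

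Neither MAR method moves, so their agreement says nothing about the departure.

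**Step 3: how large would a departure have to be?** Inputs from SAP 3.2: "2-sided significance test level of 0.05 and common standard deviation (SD) of 17.8" percent; completers "20 subjects to etrasimod 3 mg, 5 subjects to etrasimod 2 mg, and 10 subjects to placebo from Cohort 2"; and "Assuming a 15% drop-out rate from the study over 24 weeks, at least 35 treatment completers". The completer counts imply slightly more dropout than 15%: (24 - 20)/24 = 16.7%.

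The plan's own figure first. SAP 3.2 says the numbers "will provide at least 80% and 47% power to detect a treatment difference of 20" percent. With a two-sample t-test (noncentral t, df = n1 + n2 - 2):

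- 3 mg: SE = 17.8 × √(1/20 + 1/10) = 6.89; power 79.97%.
- 2 mg: SE = 17.8 × √(1/5 + 1/10) = 9.75; power 47.6%.

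Both reproduce.

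Now the tipping point for 3 mg. The smallest significant difference at 28 df is 2.048 × 6.894 = 14.12. An observed difference of 20 leaves a margin of 20 - 14.12 = 5.88. If a fraction m of the active arm is missing and those values are worsened by delta, the difference falls by m × delta.

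- Delta 10: 0.15 × 10 = 1.5 and 0.167 × 10 = 1.7 points.
- Tipping delta: 5.88/0.15 = 39 and 5.88/0.167 = 35 points.

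The deltas are assumptions, placebo stays under MAR, and the SE is held at its planned value.

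**The case against.** The strongest reply is that this is a duplicate table in an exploratory Phase 2 study with no formal testing strategy (SAP 5.6), and that the plan is not blind to missing data. Four parts of it have weight.

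- The responder endpoints are thresholds of the same percent change, at the same visit and in the same analysis set. Their main analysis is not MAR, and SAP 10.2 contrasts NRI with MI and with observed cases. This stands as partial information. It does not test the continuous estimate.
- The MMRM and MI do not simply give dropouts the average regrowth of those who stayed. They condition on each subject's own earlier SALT I, so lack of effect visible before exit is used. This stands. What remains untested is any worsening that earlier scores do not predict.
- Missing data are limited by design. Protocol 8.1 and 9.5 ask subjects to continue visits after stopping drug, and SALT I is due at early termination and is windowed under SAP 4.3. This reduces the problem, but SAP 3.2 still plans for 15% leaving the study.
- Analyses 3 to 7 answer other questions: deviations, analysis set, cohort, arm. They are useful for those and should stay. The point is only that none of them varies MAR.

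None of this makes analysis 2 informative for the continuous endpoints.

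**Conclusion.** The point holds for percent change and change from Baseline in SALT I. Analysis 2 returns the primary treatment differences by construction, and none of the other six analyses varies MAR. No planned estimate is wrong; the gap is in what the sensitivity analyses can show. On the illustrative figures, a 20-point difference at the planned floor tolerates a shift of 35 to 39 points among etrasimod dropouts.

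Three stronger readings are tempting, and the documents do not support them:

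- A reader might infer that power falls from 80% to 66%, by taking 0.85 × 20 = 17 points at 20 v 10. That pairs a difference diluted by imputed dropouts with a completers-only sample. With dropouts included, 24 v 12 gives 75% at 17 points, ignoring imputation variance. SAP 3.2 also states 20 v 10 as a minimum, to which Cohort 1 subjects with SALT I < 95 are added in a number it does not give. Power is in any case not the measure of a sensitivity analysis.
- A reader might infer that the primary estimate is biased. The documents assume one dropout rate and give no evidence of differential dropout.
- A reader might infer that NRI in the mFAS is redundant too. It is not: subjects without a post-randomization value leave the denominator.

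**What to change.** For percent change and change from Baseline in SALT I, replace sensitivity analysis 2 with a delta-adjusted tipping-point analysis. Keep NRI in the mFAS for the responder endpoints.

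- Start from the 100 imputed data sets of analysis 1. Worsen the imputed Week 24 values in each etrasimod arm by a pre-stated range of deltas, for example 0 to 40 percentage points for percent change, with a corresponding range in SALT I points for change from Baseline. Leave placebo imputations under MAR.
- Rerun the same ANCOVA and Rubin combination. Report the delta at which each dose-versus-placebo conclusion changes.
- State whether shifted values are capped at the SALT I maximum of 100. For a baseline of 94 with no change, a shift of 40 percentage points would give 94 × 1.40 = 131.6.
- Optionally add a placebo-reference imputation. This needs a changed imputation model, and a regression model is preferable to predictive mean matching with k = 5 if the placebo donor pool is too small.

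The cost is modest extra programming and a revised table. The primary analysis does not change, and the result remains exploratory.
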